6.0 TREATMENT PLAN

This study is a single-center, open-label phase 1/2 study of sorafenib in combination with G-CLAM for adults with newly diagnosed AML or high-risk MDS/MPN at the Fred Hutchinson Cancer Research Center/University of Washington. It will employ a 6+6 dose escalation rule in phase 1 and a Simon 2-stage design in phase 2 as described in Section 15.

Study Overview

After study enrollment, patients will receive a first cycle of G-CLAM + sorafenib at one designated dose level. Post-induction bone marrows will be reassessed upon blood count recovery or between day Days +28 to +35 after start of chemotherapy, whichever occurs first, unless otherwise dictated by the patient's course of clinical treatment. If the patient remains without count recovery (defined as ANC <500/ μ L and platelet count <50,000/ μ L) in the setting of an aplastic marrow (with <5% blasts), the next course of therapy will be held until (a) until bone marrow blasts are \geq 5% OR (b) the patient has count recovery to ANC >500/ μ L and platelet count >50,000/ μ L. Patients with MRDneg CR can go on to receive up to 4 courses of post-remission therapy with G-CLA + sorafenib (i.e. with same regimen as used during induction but omission of mitoxantrone). Patients with partial remission (including MRDpos CR, CR with incomplete platelet recovery [CRp], CR with incomplete count recovery[CRi]) or persistent AML are eligible to receive a 2nd course identical to induction provided any extra-medullary toxicities have resolved to \leq grade 2 with appropriate dose reductions if extra- medullary toxicities \geq grade 3 occurred during cycle 1. Patients in MRDpos CR, CRp or CRi after a 2nd course may receive a 3rd course with G-CLA + sorafenib (mitoxantrone omitted) at their current dose level. Patients still not in MRDneg CR after this 3rd course are removed from study. Patients with MRDneg CR after completion of post-remission therapy are eligible to receive maintenance therapy for up to 1 year with daily sorafenib at the final dose they received during induction,

with subsequent dose adjustments if necessary based on cytopenias and extra-medullary toxicities.

6.1 **Baseline/Pre-Treatment Assessment**

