6.6 Assessment for Response after First Induction Course

A bone marrow aspirate should be obtained upon blood count recovery (i.e. ANC >1,000/ μ L and platelet count >100,000/ μ L) or between Days +28 to +35 after start of G-CLAM chemotherapy, whichever occurs first; unless otherwise dictated by the patient's course of clinical treatment (e.g. can be delayed per treating physician discretion if clinically indicated). A bone marrow biopsy need only be obtained during this procedure if spicules are absent from the aspirate sample.. MRD will be defined in all response assessments by evidence of disease on flow cytometry at any level greater than zero.

- 6.6.1** Patients achieving MRDneg CR: Patients are eligible to receive up to 4 courses of post-remission therapy with G-CLAM + sorafenib (mitoxantrone omitted).
- 6.6.2** Patients achieving an MRDpos CR: Patients are eligible for a second course of therapy using the same dosing guidelines as course 1 (e.g. G-CLAM and Sorafenib given days 10-19) on their assigned dose level. If they again achieve an MRDpos CR, they can go on to receive a 3rd course, per discretion of the treating physician, with mitoxantrone omitted for course 3. If an MRDneg CR is not achieved after course 3, they will be removed from the study.
- 6.6.3** Patients with CRi/CRp: Patients with incomplete blood count or platelet recovery, regardless of MRD status, are eligible for a second course of therapy using the same dosing guidelines as course 1 (e.g. G-CLAM and Sorafenib given days 10-19) on their assigned dose level. If they again achieve a CRi/p (regardless of MRD), they can go on to receive a 3rd course, per discretion of the treating physician, with mitoxantrone omitted for course 3. If an MRDneg CR is not achieved after course 3, they will be removed from the study.
- 6.6.4** Patients with persistent disease: Patients with persistent AML ($\geq 5\%$ blasts) are eligible for a second course of induction chemotherapy at the same dosing used in course 1 (e.g. G-CLAM and Sorafenib given days 10-19) on their assigned dose level, provided all non-hematologic toxicities have resolved to Grade <2. If they are not in CR after the 2nd induction course, they can go on to receive a 3rd course, per discretion of the treating physician, with mitoxantrone omitted for course 3. If an MRDneg CR is not achieved after course 3, they will be removed from the study.

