- 6.6.5** Patients with persistent aplasia without evidence of disease after Day +49: patients will be removed from protocol.
- 6.6.6** For patients who experienced \geq Grade 3 non-hematologic toxicities excluding neutropenic fever and infections during the first induction, dose reductions are allowed but not required for this cycle as discussed in section 6.10.

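### The hold on the next course applies only when ANC and platelets are both low, although its own release clause and sections 6.14.5 and 8.3.3 treat either low count as non-recovery

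*Combined protocol and SAP*

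**What the plan says.** **Trigger.** The Study Overview in section 6.0 sets a hold on the next course for patients whose marrow is aplastic with fewer than 5% blasts: "If the patient remains without count recovery (defined as ANC <500/ μ L and platelet count <50,000/ μ L". Both counts must be low.

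**Release.** The same sentence ends the hold when blasts reach 5% or, on counts, when "the patient has count recovery to ANC >500/ μ L and platelet count >50,000/ μ L". Both counts must have recovered.

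**Other rules on the same limits.** Section 6.14.5 (removal for persistent aplasia after Day +49) and section 8.3.3 (hematologic DLT, more than 49 days from the start of G-CLAM) use the same limits of 500 and 50,000. Both join them with *or*. Section 6.6.5 gives the consequence after the first induction: "Patients with persistent aplasia without evidence of disease after Day +49: patients will be removed from protocol". Section 6.7.3 repeats it after the second.

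**Access to the next course.** Section 6.6.3 says: "Patients with incomplete blood count or platelet recovery, regardless of MRD status, are eligible for a second course of therapy". It names no minimum count. Section 6.7.2 opens a third course to patients with CRi/CRp after course 2, again without one. The Overview's other condition on course 2 concerns extra-medullary toxicity: such patients "are eligible to receive a 2nd course identical to induction provided any extra-medullary toxicities have resolved to" Grade 2 or lower.

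**Timing.** Under section 6.6 the response marrow is taken "upon blood count recovery (i.e. ANC >1,000/ μ L and platelet count >100,000/ μ L") or between Days +28 and +35, whichever comes first. It "can be delayed per treating physician discretion if clinically indicated".

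**The concern.** A trigger and its release should be complements: a patient who does not meet the release condition should be one whom the trigger catches. Here they are not. With one lineage low, the hold never starts, yet had it started it could not be lifted on counts.

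Two things are at stake. The first is safety, in both phases. A patient with fewer than 5% blasts and, say, platelets of 30,000 is outside the hold and may receive another myelosuppressive course. The second is dose finding in phase 1. Section 8.3.3 is the only hematologic DLT and cannot be met until more than 49 days have passed. If course 2 has started by then, continuing cytopenia can no longer be cleanly attributed to course 1.

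**Working it through.** The plan gives no figure on this point, so there is none to reproduce. The check sets the rules side by side and then does a calendar subtraction.

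**1. The four count patterns.** The limits are ANC 500/µL and platelets 50,000/µL (sections 6.0, 6.14.5 and 8.3.3). One illustrative value is taken on each side of each limit, with an aplastic marrow throughout.

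| ANC | Platelets | Held (both low) | Release met (both recovered) | Low by 6.14.5 / 8.3.3 (either low) |
|---|---|---|---|---|
| 300 | 30,000 | yes | no | yes |
| 300 | 70,000 | **no** | **no** | **yes** |
| 700 | 30,000 | **no** | **no** | **yes** |
| 700 | 70,000 | no | yes | no |

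The trigger holds 1 of 4 patterns. The release clause is unmet in 3 of 4, and the *or* definition flags 3 of 4. The rules disagree in 3 − 1 = 2 patterns, exactly those with one low lineage.

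The mismatch with the release clause applies whatever the MRD status. The comparison with sections 6.14.5 and 8.3.3 bears on patients without evidence of disease, since both rules require that. Section 6.6 sets the standard for this: "MRD will be defined in all response assessments by evidence of disease on flow cytometry at any level greater than zero".

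**2. Whether another rule closes the gap.**
- Section 6.6.3: no minimum count for course 2.
- Section 6.7.2: no minimum count for course 3.
- Section 6.8.2: requires recovery of toxicity, but for post-remission courses only.
- Section 6.10.1: delays the next G-CLAM course for non-hematologic toxicity only.
- Sections 6.6.5, 6.7.3 and 6.14.5: act only after Day +49.

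None of them stops a next course at Day 28 to 35 on counts.

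**3. The interval before the DLT can be read.** The first day beyond 49 days is Day 50, taking the plan's day numbers as days from the start of G-CLAM. From a Day 35 marrow the gap is 50 − 35 = 15 days. From a Day 28 marrow it is 50 − 28 = 22 days. These are the longest gaps the scheduled window allows, if course 2 starts on the day of the marrow. They are not expected intervals.

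**4. After changing the trigger to *or*.** It holds 3 of 4 patterns, so the mismatch with the release clause falls from 2 of 4 to 0 of 4. Only values exactly on a limit remain undefined, because the trigger uses *below* and the release uses *above*. No sample size or error rate changes.

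**The case against.** The strongest reply is that this is a drafting slip and is readable in context. The sentence itself says what recovery is, so an ordinary reader would take a patient who falls short of it as being without recovery and would hold that patient. This is probably what was meant. It lowers the weight of the point, but the sentence is an operative dosing rule with an explicit definition, and a clinician who follows that definition does not hold the patient. A deliberately asymmetric rule is also conceivable, but no section states one.

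The second reply is that clinical judgment will usually prevent harm. Course 2 is an option, the marrow can be delayed, and section 6.10.1 lets mitoxantrone be left out of a second induction after Grade 3 or higher non-hematologic toxicity. All of this stands. It makes the event less likely but does not correct the rule.

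The third reply is that 2 of 4 counts logical patterns, not patients. This also stands.

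A reader might also infer that two patients with identical counts receive opposite instructions, one held and one not. That requires the held patient to have had an aplastic marrow on an earlier date, when both counts were low. Section 6.6 asks for one response aspirate, so the case has to be constructed, and the point does not need it.

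**Conclusion.** The inconsistency is real and should be fixed. In the literal text the trigger disagrees with its own release clause and with two other sections in 2 of 4 count patterns. No other rule sets a minimum count for course 2, which could begin up to 15 to 22 days before section 8.3.3 can be read. Confidence is high for this mismatch and does not extend to its consequences.

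A reader might infer that hematologic DLTs will be missed and that escalation will therefore be too aggressive. The documents do not support this. They do not say how often a single lineage stays low with an aplastic marrow, or how often course 2 would be given then. The direction is also open. Section 14.1.1 uses DLTs arising in Cycle 1, which suggests that cytopenia under course 2 would not count. Section 8.3.3 counts days from the start of G-CLAM, which suggests that it could. Nor do the documents support reading the plan as requiring re-treatment, since section 6.6.3 gives eligibility only.

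The conclusion assumes a literal reading of the trigger and marrow assessment within the scheduled window.

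**What to change.** In the Study Overview of section 6.0, define the trigger as ANC below 500/µL **or** platelets below 50,000/µL. It then complements the release clause, apart from exact boundary values, and matches sections 6.14.5 and 8.3.3. In sections 6.6.3 and 6.7.2, add that eligibility for the next course is subject to this hold. Patients with CRi/CRp whose counts are above 500 and 50,000 but short of full recovery stay eligible as now.

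The drafting cost is one word and two short cross-references. The clinical cost is that some patients with one low lineage wait longer for the next course. This includes MRD-positive patients with fewer than 5% blasts, because the hold does not look at MRD. Patients still low after Day +49 without evidence of leukemia leave under the existing sections 6.6.5, 6.7.3 and 6.14.5. A few may thus lose a second induction, whose result the phase 2 endpoint in section 14.2 (MRDneg CR after up to 2 courses) would have counted. That could lower the number of responders set against the fixed cut-offs of 12/19 and 31/41. The documents give no basis for sizing this.

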6.6 Assessment for Response after First Induction Course

A bone marrow aspirate should be obtained upon blood count recovery (i.e. ANC >1,000/ μ L and platelet count >100,000/ μ L) or between Days +28 to +35 after start of G-CLAM chemotherapy, whichever occurs first; unless otherwise dictated by the patient's course of clinical treatment (e.g. can be delayed per treating physician discretion if clinically indicated). A bone marrow biopsy need only be obtained during this procedure if spicules are absent from the aspirate sample.. MRD will be defined in all response assessments by evidence of disease on flow cytometry at any level greater than zero.

- 6.6.1** Patients achieving MRDneg CR: Patients are eligible to receive up to 4 courses of post-remission therapy with G-CLAM + sorafenib (mitoxantrone omitted).
- 6.6.2** Patients achieving an MRDpos CR: Patients are eligible for a second course of therapy using the same dosing guidelines as course 1 (e.g. G-CLAM and Sorafenib given days 10-19) on their assigned dose level. If they again achieve an MRDpos CR, they can go on to receive a 3rd course, per discretion of the treating physician, with mitoxantrone omitted for course 3. If an MRDneg CR is not achieved after course 3, they will be removed from the study.
- 6.6.3** Patients with CRi/CRp: Patients with incomplete blood count or platelet recovery, regardless of MRD status, are eligible for a second course of therapy using the same dosing guidelines as course 1 (e.g. G-CLAM and Sorafenib given days 10-19) on their assigned dose level. If they again achieve a CRi/p (regardless of MRD), they can go on to receive a 3rd course, per discretion of the treating physician, with mitoxantrone omitted for course 3. If an MRDneg CR is not achieved after course 3, they will be removed from the study.
- 6.6.4** Patients with persistent disease: Patients with persistent AML ($\geq 5\%$ blasts) are eligible for a second course of induction chemotherapy at the same dosing used in course 1 (e.g. G-CLAM and Sorafenib given days 10-19) on their assigned dose level, provided all non-hematologic toxicities have resolved to Grade <2. If they are not in CR after the 2nd induction course, they can go on to receive a 3rd course, per discretion of the treating physician, with mitoxantrone omitted for course 3. If an MRDneg CR is not achieved after course 3, they will be removed from the study.
- 6.6.5** Patients with persistent aplasia without evidence of disease after Day +49: patients will be removed from protocol.
- 6.6.6** For patients who experienced \geq Grade 3 non-hematologic toxicities excluding neutropenic fever and infections during the first induction, dose reductions are allowed but not required for this cycle as discussed in section 6.10.

6.7 Assessment for Response after a Second Induction Course

If a patient receives a second induction course (s per section 6.6.2-6.6.4), a bone marrow aspirate should again be obtained upon blood count recovery (i.e. ANC >1,000/ μ L and platelet count >100,000/ μ L) or between Days +28 to +35 after start of G-CLAM chemotherapy, whichever occurs first, unless otherwise dictated by the patient's course of clinical treatment. A bone marrow biopsy need only be obtained during this procedure if spicules are absent from the aspirate sample.

- 6.7.1** Patients achieving MRDneg CR: Patients are eligible to receive up to 4 courses of post-remission therapy with G-CLA + sorafenib (mitoxantrone omitted).
- 6.7.2** All other patients (MRDpos CR, CRI/CRp, persistent disease): Patients are eligible for a third course of therapy, per discretion of the treating physician, with mitoxantrone omitted for course 3 (G-CLA) and Sorafenib given on days 8-27 or 3 days prior to next cycle of treatment, whichever occurs first. **If an MRDneg CR is not achieved after course 3, they will be removed from the study.**
- 6.7.3** Patients with persistent aplasia without evidence of disease after Day +49: patients will be removed from protocol.

6.8 Post-Remission Therapy

After achievement of an MRDneg CR with G-CLAM+sorafenib, patients are eligible for post-remission therapy with G-CLA+sorafenib.

- 6.8.1** The treatment is identical to the induction course but without mitoxantrone (i.e. G-CSF, cladribine, and cytarabine, or "G-CLA" + sorafenib, at same dose level as induction). If that patient had excessive toxicities (grade ≥ 3 non-hematologic toxicity excluding neutropenic fever and infections) during induction, doses should be reduced as described in section 6.10.
- 6.8.2** Post-remission courses should start within 6 weeks of achieving CR once patients have recovered to \leq Grade 2 toxicities from the previous course of therapy.
- 6.8.3** Patients can receive up to 4 courses of post-remission therapy.
- 6.8.4** Patients can proceed to transplantation barring contraindications and if a suitable donor is available.

6.9 Maintenance Therapy

- 6.9.1** Patients in MRDneg CR at the end of post-remission therapy with G-CLA+sorafenib can continue to receive sorafenib for up to 12 months, as long as it is tolerated and as long as an MRDneg CR is maintained. Sorafenib will be given daily at the assigned dose level, unless dose reductions are needed for toxicity, in which case that dose would be continued. The MRDneg CR state should be confirmed every 3 months with bone marrow evaluations.

6.10 Dose Modifications of Chemotherapeutic Drugs for Baseline Organ Dysfunction or Subsequent Treatment Cycles

For patients with baseline organ dysfunction within the allowed limits of the eligibility criteria, or for those who experienced \geq Grade 3 non-hematologic toxicities excluding neutropenic fever and infections during the first induction, a dose reduction is

recommended. The following dose modifications are suggested for all subsequent treatment cycles:

6.10.1 If a patient develops Grade ≥ 3 non-hematologic toxicity other than Grade 3 infections within 28 days from the last dose of G-CLAM, the next course of G-CLAM will be given once toxicity is $<$ grade 2. The following dose reductions can be considered: cladribine 4 mg/m² days 1-5, cytarabine 1.5 g/m² days 1-4, mitoxantrone at one dose level below initial regimen days 1-3, G-CSF dose unchanged, and sorafenib at one dose level below their initial regimen. Additionally, the mitoxantrone may be omitted entirely if a 2nd induction course is indicated (any response less than CR without MRD) per treating physician discretion in discussion with the PI. Assuming these doses are well-tolerated the first course of G-CLA will be administered at these doses, omitting mitoxantrone. If Grade ≥ 3 non-hematologic toxicity occurs again, there will be a further reduction in doses of cladribine to 3 mg/m² daily days 1-5 and cytarabine to 1 g/m² daily days 1-5 for the first cycle of G-CLA. Doses for subsequent courses of G-CLA will be discussed with the Principal Investigator. Patients who were receiving dose level -1 sorafenib or mitoxantrone when grade ≥ 3 toxicity occurred will be taken off study.

6.10.2 Mitoxantrone: Reduce mitoxantrone dose by 50% if the bilirubin concentration is 1.5-4.5 x IULN and to 25% if the bilirubin concentration is > 4.5 x IULN. As per 6.10.1 can omit mitoxantrone entirely if clinically indicated.

6.10.3 Cladribine: If the serum creatinine exceeds 2.0 mg/dL and/or estimated creatinine clearance (calculated by Cockcroft-Gault) decreases to less than 50 mL/min during therapy, we will consider dose reduction in discussion with the Oncology Pharmacist.

6.10.4 Cytarabine: If the serum creatinine exceeds 2.0 mg/dL and/or estimated creatinine clearance (calculated by Cockcroft-Gault) decreases significantly during therapy, we will consider dose reduction in discussion with the Oncology Pharmacist.

6.10.5 Sorafenib: If transaminitis occurs with liver function tests exceeding 6 x IULN with concurrent hyperbilirubinemia (bilirubin concentration > 4.5 x IULN), and any evidence of hepatic injury such as elevated INR and ascites, sorafenib should be held/discontinued. Further therapy should be resumed based on physician discretion after discussion with Principal Investigator and the Oncology Pharmacist.

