- 6.3.1 For induction: patients will receive sorafenib and mitoxantrone at 1 of 6 total dose levels as allocated (see section Dose Escalation Scheme page 2 or 15.1.2). Mitoxantrone will be given IV daily over 60 minutes Days 1-3 and sorafenib orally Days 10-19 for all levels. Allowances of +/- 2 days for this window will be allowed for logistical purposes. Levels are as follows: Level 1, mitoxantrone 10 mg/m² with sorafenib 200 mg PO twice daily; Level 2, mitoxantrone 12 mg/m² with sorafenib 200 mg PO twice daily; Level 3, mitoxantrone 15 mg/m² with

sorafenib 200 mg PO twice daily; Level 4, mitoxantrone 18 mg/m² with sorafenib 200 mg PO twice daily; Level 5, mitoxantrone 18 mg/m² with sorafenib 400 mg PO in the morning and 200 mg in the evening; Level 6, mitoxantrone 18 mg/m² with sorafenib 400 mg PO twice daily. Level -1, dosed at mitoxantrone 10 mg/m² and sorafenib 200 mg PO once daily will also be available for dose de-escalation due to toxicities, as described in Section 6.8. For baseline organ dysfunction within the allowable limits of the eligibility criteria, dose reduction of individual medications specific to the organ impairment (e.g. liver, kidney) are allowed but not required, as described in section 6.10, and should be done in conjunction with the Oncology Pharmacist and PI.

- 6.3.2 The dose of mitoxantrone is calculated using the patient's actual weight.
- 6.3.3 For post-remission therapy: sorafenib will be given per dose level as above, starting on day 8 until day 27 or 3 days prior to next cycle of treatment, whichever occurs first. Allowances of +/- 3 days for this window will be allowed for logistical purposes (i.e. timing of clinic visit for count evaluation).
- 6.3.4 For maintenance: sorafenib will be given daily for up to 12 months following post-remission at the final dose the patient received during induction, with subsequent dose adjustment based on blood counts and extra-medullary toxicities.
- 6.3.5 All treatment is given as intent-to-treat; missed doses will not be made up.

6.4 **Administration of G-CSF, Cladribine, and Cytarabine**

- 6.4.1 The doses of the elements of G-CLAM chemotherapy will be as follows: G-CSF 5 µcg/kg rounded to 300 or 480 µcg daily subcutaneously daily on Days 0-5, Cladribine 5 mg/m² IV daily over 2 hours on Days 1-5, and Cytarabine 2 g/m² IV daily over 2 hours on Days 1-5.
- 6.4.2 The doses of G-CSF, cladribine, and cytarabine are calculated using the patient's actual weight.

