APPENDIX D: MANAGEMENT OF TOXICITIES SPECIFIC TO SORAFENIB

I. Prevention/management strategies for diarrhea and fatigue

Diarrhea and fatigue are common side effects of sorafenib. The same dose-modification algorithm used for skin toxicities can be used to address these toxicities. However, the preventive/management strategies for diarrhea and fatigue should be consistent with local standards (e.g., anti-diarrheals and optimized hydration status for diarrhea).

II. Hand-foot-skin reaction: Suggested sorafenib dermatologic toxicity modification

Recommended dose modification for hand foot skin reaction (HFSR)		
Toxicity Grade		Suggested dose modification
Grade 1	Any occurrence	Maintain dose level and consider topical therapy for symptomatic relief
Grade 2	1 st occurrence	Maintain dose level and consider topical therapy for symptomatic relief If no improvement within 7 days, see below
	No improvement within 7 days or 2 nd occurrence	Interrupt until resolved to Grade 0-1 When resuming treatment, decrease dose by one dose level
	3 rd occurrence	Interrupt until resolved to Grade 0-1 When resuming treatment, decrease dose by two dose levels
	4 th occurrence	Discontinue treatment permanently
Grade 3	1 st occurrence	Interrupt until resolved to Grade 0-1 When resuming treatment, decrease dose by one dose level
	2 nd occurrence	Interrupt until resolved to Grade 0-1 When resuming treatment, decrease dose by two dose levels
	3 rd occurrence	Discontinue treatment permanently

At first occurrence of HFSR, independent of grade, prompt institution of supportive measures such as topical emollients, low potency steroids, or urea-containing creams should be administered.

Recommended prevention/management strategies for skin toxicities consistent with HFSR are summarized below.

Recommended Prevention/Management Strategies for Skin Toxicities Consistent with Hand-Foot-Skin-Reaction	
Toxicity Grade	Practical Prevention / Management Strategies for HFSR
Grade 0 (Preventive strategies)	
 • Maintain frequent contact with trial physician to ensure early diagnosis of HFSR. • Practical prevention strategies 
 ◦ Pedicure^a for subjects with pre-existing hyperkeratosis. ◦ Subjects should avoid hot water, and clothing or activities that can cause friction on the skin. ◦ Moisturizing cream should be applied sparingly. • Padded gloves and open shoes with padded soles should be worn to relieve pressure points.

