Grade 4	Discontinue sorafenib

a: Subjects requiring a delay of > 30 days (modify according to study specific cycle length) should discontinue sorafenib unless, in the opinion of the treating physician, the subject may benefit from continued treatment.

b: Subjects requiring dose reductions beyond 200 mg (1 placebo tablet) twice daily, every other day, should discontinue sorafenib.

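### Dose level is defined as a mitoxantrone–sorafenib pair but used as a per-drug reduction step, so some sorafenib decreases change nothing and the level -1 rules conflict

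*Combined protocol and SAP*

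**What the plan says.** The dose table at the front of the protocol, Section 6.3.1 and Section 14.1.2 give the same ladder. Section 6.3.1 states that "patients will receive sorafenib and mitoxantrone at 1 of 6 total dose levels as allocated", and each level names both drugs: "Level 1, mitoxantrone 10 mg/m² with sorafenib 200 mg PO twice daily", then at level 2 "mitoxantrone 12 mg/m² with sorafenib 200 mg PO twice daily", and so on to level 6. Level -1 pairs mitoxantrone 10 mg/m² with sorafenib 200 mg once daily. No ladder for a single drug appears anywhere.

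Four passages then use the term for reductions:

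- Section 6.10.1, after Grade 3 or higher non-hematologic toxicity, lists among reductions that may be considered "mitoxantrone at one dose level below initial regimen days 1-3" and "sorafenib at one dose level below their initial regimen". It also lets mitoxantrone be left out of a second induction.
- Section 6.8.1 says that post-remission doses should be reduced by reference to Section 6.10 if induction was too toxic.
- Appendix D, part II (hand-foot skin reaction) steps sorafenib down by one level or, on later occurrences, "When resuming treatment, decrease dose by two dose levels". Part I allows the same scheme for diarrhea and fatigue. Part III (hypertension) steps sorafenib down one level, then another if pressure is not controlled.
- The off-study sentence of Section 6.10.1 begins "Patients who were receiving dose level -1 sorafenib or mitoxantrone when grade" and requires removal when toxicity is Grade 3 or higher.

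Footnote b to the hypertension table sets a floor: "Subjects requiring dose reductions beyond 200 mg (1 placebo tablet) twice daily, every other day, should discontinue sorafenib".

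**The concern.** Above level -1 the ladder changes one drug per step: mitoxantrone from level 1 to level 4, sorafenib from level 4 to level 6. The step from level 1 to level -1 changes sorafenib only. An instruction to take sorafenib down one level can therefore point to a row with the same sorafenib dose. In the post-remission table, rows 1 to 4 are identical for every drug, and in maintenance sorafenib is the only drug, so there the ladder offers no second drug whose dose falls instead.

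Two things are at stake. A patient with a sorafenib toxicity could resume at the dose on which it occurred. And two members of staff could read the same sentence and give different doses. Course 2 lies inside the window of the primary endpoint (Section 14.2 counts up to two induction courses), so part of the exposure behind that endpoint rests on an undefined term. At the bottom of the ladder, two passages give different instructions for the same patient.

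**Working it through.** Inputs, from the front dose table and Sections 6.3.1 and 14.1.2. Sorafenib per day is the sum of the two doses: 200 + 200 = 400 mg at levels 1 to 4; 400 + 200 = 600 mg at level 5; 400 + 400 = 800 mg at level 6; 200 mg at level -1. Mitoxantrone is 10, 12, 15, 18, 18 and 18 mg/m² at levels 1 to 6, and 10 at level -1. Steps are counted from the assigned level.

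Reading A: the stated definition, moving down rows of the joint table.

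| From | One down | Mitoxantrone, mg/m² | Sorafenib, mg/day | Sorafenib two down, mg/day |
|---|---|---|---|---|
| 6 | 5 | 18 → 18 | 800 → 600 | 400 (level 4) |
| 5 | 4 | 18 → 18 | 600 → 400 | 400 (level 3) |
| 4 | 3 | 18 → 15 | 400 → 400 | 400 (level 2) |
| 3 | 2 | 15 → 12 | 400 → 400 | 400 (level 1) |
| 2 | 1 | 12 → 10 | 400 → 400 | 200 (level -1) |
| 1 | -1 | 10 → 10 | 400 → 200 | no such level |

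One level down, sorafenib does not fall from levels 2, 3 and 4, and mitoxantrone does not fall from levels 1, 5 and 6. Two levels down, sorafenib does not fall from levels 3 and 4. From level 5, one and two levels down give the same 400 mg/day.

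Reading B: unstated; each drug moves to its own next lower tabulated dose (mitoxantrone 18, 15, 12, 10; sorafenib 800, 600, 400, 200).

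| From | Mitoxantrone one down | Sorafenib one down | Sorafenib two down |
|---|---|---|---|
| 6 | 15 | 600 | 400 |
| 5 | 15 | 400 | 200 |
| 4 | 15 | 200 | none |
| 3 | 12 | 200 | none |
| 2 | 10 | 200 | none |
| 1 | none | 200 | none |

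Both drugs now fall from levels 2 to 6. Mitoxantrone has no step from level 1, and a two-level sorafenib cut has no tabulated destination from levels 1 to 4.

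The readings give different doses. One level down, sorafenib is 400 under A and 200 under B from levels 2 to 4, and mitoxantrone is 18 under A and 15 under B from levels 5 and 6.

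The lowest level. For a patient at level -1 with Grade 3 hand-foot skin reaction (first or second occurrence) or Grade 3 hypertension, Section 6.10.1 requires removal from study. Appendix D says to interrupt or hold sorafenib and resume lower, though no lower level exists. The hypertension floor of 200 mg twice daily every other day averages (2 × 200) / 2 = 200 mg/day. That equals the level -1 average, but the schedule is not in the dose table.

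**The case against.** The best reply is that a per-drug meaning was plainly intended. Section 6.10.1 gives the drugs separate clauses and speaks of level -1 of one drug or the other, and telling a site to decrease a dose makes little sense if the dose stays the same. This carries weight: under Reading B most of the difficulty at levels 2 to 6 goes. A reader might infer that the rules flatly contradict the table. That goes too far, because the text admits a reading that mostly works. But that reading is nowhere stated, and it still fails at the places shown above.

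Discretion is the second reply. The 6.10.1 cuts are optional, Section 6.6.6 does not require them for a second induction, mitoxantrone can be omitted, and fixed cladribine and cytarabine cuts are listed as well. This largely disposes of the mitoxantrone half, which matters only for a second induction because post-remission courses omit the drug. It does not settle sorafenib: Section 6.8.1 says post-remission doses should be reduced, and discretion over whether to reduce does not define the step.

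Third, the medication diary is pre-filled with sorafenib 400 mg twice daily, the level 6 dose. If later patients are all treated there, the two readings agree for sorafenib (600, then 400 mg/day). This limits the practical reach, but a form is not proof of who is treated at which level.

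Three other inferences are not supported. A level 1 patient receives the level -1 mitoxantrone dose, which might suggest that the off-study rule removes that patient; but the patient was allocated to level 1, and Section 6.3.1 makes level -1 available for de-escalation, so the text is unclear and removal is not established. That one drug stays put from all six starting levels is mostly a restatement of a ladder that moves one drug at a time; each step still lowers the other. And the every-other-day floor belongs to the hypertension table, not to the whole of Appendix D.

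**Conclusion.** The point stands as an undefined term with consequences for safety instructions. By the only definition given, the sorafenib decrease is empty for one step from levels 2 to 4 and for two steps from levels 3 and 4. The drug-by-drug alternative is incomplete as well as unstated. Separately, Section 6.10.1 and Appendix D conflict for a level -1 patient with Grade 3 hand-foot skin reaction or hypertension, and it is unclear whether the off-study rule reaches level 1.

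This rests on two assumptions: that the joint table is the sole definition, since no other could be found, and that Appendix D counts steps from the assigned level, which it does not say. No effect on the rate of complete remission without residual disease is estimated or claimed. The two-stage design, its sample size and its error rates are not affected. The correction should be made, but the point does not put the design in question.

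**What to change.** Reconcile Sections 6.8.1 and 6.10.1, Appendix D and the dose tables. For each drug, state a separate sequence of reduction steps, a single floor and a single off-study rule, and refer to these wherever reductions are now expressed in dose levels. Say whether a two-level step counts from the assigned or the current dose, what happens when no lower step remains, and whether the off-study rule covers level 1 patients. Keep dose level for the joint escalation cohorts only. The doses and the clinical rules are for the sponsor to set.

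The cost is one short table and a few cross-references in an amendment. While doing this, correct the pointer in Section 6.3.1, which sends the reader to Section 6.8 for de-escalation although the modifications are in Section 6.10.
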